## 6.3 QUALITY OF LIFE ASSESSMENTS (Secondary Objectives)

- 6.3.1 FACT-G: Functional Assessment of Cancer Therapy - General version of the scale constitutes the core of all subscales. FACT-G can be used with patients of any tumor type. It measures generic health status relevant across different age, disease, and treatment groups. It provides a comprehensive, psychometrically sound

assessment of health status from the patient's point of view by scoring responses to standard questions. The FACT-G is self-administered, and can usually be completed in less than 3 minutes without assistance.

6.3.2 EXPANDED PROSTATE CANCER INDEX COMPOSITE (EPIC)-26: is a validated comprehensive instrument developed to assess patient function and bother after prostate cancer treatment. It was developed by an expert panel of urological oncologists, radiation oncologists (including those with brachytherapy expertise), survey researchers, and prostate cancer nurses, to address symptoms related to radical prostatectomy, external beam radiotherapy, prostate brachytherapy, and hormonal symptoms. See appendix III.

6.3.3 AMERICAN UROLOGICAL ASSOCIATION (AUA) SYMPTOM INDEX: Also known as the International Prostate Symptom Score (IPSS), this widely used index assesses urinary symptom bother. See appendix III.

6.3.4 SEXUAL HEALTH INVENTORY FOR MEN (SHIM): is a widely used, internationally validated and sensitive instrument for assessing erectile dysfunction.

6.3.5 UTILIZATION OF SEXUAL MEDICATIONS/DEVISES: provides context for interpreting the sexual domain score of the EPIC questionnaire.

6.4 CRITERIA FOR DISEASE CONTROL: intervals will be measured from date of first treatment.

6.4.1 (Primary Efficacy Objective) **BIOCHEMICAL DISEASE-FREE SURVIVAL (bDFS)**: is measured as time to PSA failure. While earlier reports of prostate cancer patients treated with radiotherapy have used the ASTRO consensus definition (ACD) of PSA failure, recent studies have suggested the “nadir+2” definition is a more sensitive and specific definition of biochemical failure. Indeed, a recent expert panel met in Phoenix and developed a consensus recommendation using the later definition. So that comparisons can be made with earlier literature, both definitions shall be used:

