## 7.2 SAMPLE SIZE:

7.2.1 PRIMARY SAFETY OBJECTIVE: The study is designed to test the null hypothesis that the acute and late GI/GU toxicity rate 2 years following treatment is less than 10% versus the alternative hypothesis that the toxicity rate is greater than or equal to 10%. If we end up with 200 eligible patients, there will be 99% probability, or statistical power, of identifying excessive toxicity if the true

toxicity rate is 20%, at the one-sided significance level ( $\alpha$ ) 0.05. The intervention will be considered to be safe if the acute and late GI/GU toxicity rate 2 years following treatment is not above 10%

7.2.2 PRIMARY EFFICACY OBJECTIVE: The study is powered to compare 2-year bDFS rates observed with SBRT to 2-year bDFS rates reported with dose-escalated external beam RT. In Beaumont's monotherapy HDR series treating patients, 5-yr ASTRO bDFS was 97.5%; in Demanes' series of 75% LR and 25% IR, this was 96%. We would expect Phoenix outcomes to be slightly higher than ASTRO outcomes at 5 years. Since SBRT delivers doses similar to HDR monotherapy, a conservative estimate of the success rate for SBRT is 97.5%. In LR patients, prospective studies from Memorial Sloan Kettering (203 patients, 81Gy) and MD Anderson (32 patients, 78Gy) demonstrated 5-yr bDFS (Phoenix definition) of 92% and 92%, respectively. Thames' 9-institution review of 231 dose-escalated (70-76Gy) LR patients reported 94% 5-yr Phoenix bDFS. Thus, an objective performance criteria (OPC) for low-risk patients treated with dose-escalated external beam RT is 92% 5-yr bDFS. If we assume the SBRT success rate is 97%, a sample size of 200 patients will provide 99% power to test superiority of SBRT against this OPC with 80% power at the 1-sided 5% significance level. If we assume the SBRT success rate is 96%, then the power will be 78%.

7.2.3 TOTAL AND RELATIVE ENROLLMENT: Per above sections 7.2.1-7.2.2, we plan to accrue 200 eligible patients to compare the 2-year bDFS rate observed with SBRT to the 2-year OPC rate, and to establish acceptable toxicity. The test cohort will be closed to accrual once requisite enrollment is achieved: 200 total patients.

7.2.4 ACCRUAL RATE: The accrual rate will be 5–6 patients / month over 2 years.

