## 7.3 STATISITCAL METHODS:

The *primary* objectives of this study are:

- To determine, in both low-risk and intermediate-risk cohorts, the rates of acute and late grade 3 or higher gastrointestinal and genitourinary toxicity observed during an initial 24 month follow up.
- To estimate the rate of biochemical Disease-Free Survival (bDFS), Phoenix and ASTRO definitions, at 2 years following hypofractionated SBRT for low and intermediate risk prostate cancer. Failure occurs when the PSA is  $\geq 2$  ng/ml more than the lowest PSA measurement before the current one, with no backdating.

The *secondary* objectives of this study are to:

- the rate of local failure: proportion of patients with local disease progression at 2 years

- rate of distant failure: proportion of patients with metastatic disease at 2 years
- rate of disease-free survival: median time from start of treatment until disease progression
- rate of disease-specific survival: death due to prostate cancer (excludes patients that relapse with inactive disease)
- overall survival: median length of time from either the date of diagnosis or the start of treatment for a disease, such as cancer, that patients diagnosed with the disease are still alive.
- quality of life (QOL) in generic and organ-specific domains using the FACT-G assessment tool

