### 7.3.1 PRIMARY ENDPOINTS:

Wilson score interval is used to determine the confidence intervals for the expected proportion of patients experiencing a “success” outcome.

7.3.1.1 SAFETY: The upper limit of a one-sided 95% confidence interval for the expected proportion of patients experiencing any grade 3-5 acute or late toxicity as defined above in 7.1, is estimated by U, where

$$U = \frac{(2np + Z_{0.95}^2) + Z_{0.95} \sqrt{Z_{0.95}^2 + 4np(1-p)}}{2(n + Z_{0.95}^2)}$$

where:

p: the observed proportion of patients experiencing any grade 3-5 acute or late toxicity as defined above in 7.1;  
n: the total number of patients;  
 $Z_{0.95} = 1.645$ .

The intervention will be considered to be safe if this study’s result verifies that U is not above 10%i.

7.3.1.2 EFFICACY: The lower limit of a one-sided 95% confidence interval for the expected proportion of patients experiencing biochemical disease-free survival (bDFS) is estimated by L, where

$$L = \frac{(2np + Z_{0.95}^2) - Z_{0.95} \sqrt{Z_{0.95}^2 + 4np(1-p)}}{2(n + Z_{0.95}^2)}$$

where:

p: the observed proportion of patients experiencing bDFS;  
n: the total number of patients;  
 $Z_{0.95} = 1.645$ .

The SBRT intervention will be considered to be effective if this study’s result verifies that L is not below 92%.

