### 7.3.2 SECONDARY ENDPOINTS

#### 7.3.2.1 MEASUREMENTS OF RATE OF LOCAL FAILURE

AND RATE OF DISTANT FAILURE: The PSA levels are used to quantify the rate of local and distant failures repeatedly during the post treatment period. The GEE (Generalized Estimating Equation) method will be used to

provide valid inferences. This method was originated to make inference about average behaviour, where the dependent variable depends not only on the “explanatory” variable (time measured in months) but also on the correlation of a patient’s repeated measurements. The GEE approach fits the model to the observed data as closely as possible, weighting each patient’s “cluster” of measurements over time inversely to its variance-covariance matrix. With this method, no imputations are required and all data recorded is used in the analysis. Other important features of GEE are that no distributional assumptions for the dependent variable are required to use the method and in most cases valid inferences are provided even when the correlation structure is miss-specified. For each PSA level, we will use GEE to fit a model to patients’ longitudinal course of repeated values.

7.3.2.2 **QUALITY OF LIFE ASSESSMENTS:** The FACT-G scores, AUA score, EPIC-26 scores are used to quantify quality of life (QOL) at baseline and repeatedly during the post treatment period. Similarly to measurements of local and distant failure rate, we will still use the GEE method to provide valid inferences. For each score, we will use GEE to fit a model to patients’ longitudinal course of repeated values. We hypothesize that immediately following treatment, the GU & GI subsections of the EPIC-26 and the AUA will demonstrate a worsening of GU and GI function, but this will return to normal with time. We further hypothesize that the sexual function subset of the EPIC-26 will show gradual worsening function relative to baseline over the five-year follow-up period. These QOL outcomes will be compared to those reported in other prospective studies using the same instruments, including RTOG 0232 and 0415.

7.3.2.3 **SURVIVAL ANALYSIS:** Survival analyses will be performed for the following quantities:

- Rate of disease-free survival;
- Rate of disease-specific survival;
- Overall survival for death from any cause;

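### Two-year bDFS is defined as a time to failure but tested as a crude proportion over all patients, with no censoring and no rule for men without 24-month status; the safety proportion misses toxicity that occurs after loss

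*Combined protocol and SAP*

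**What the plan says.** Section 6.4.1 states that bDFS "is measured as time to PSA failure". Section 6.4 measures intervals from first treatment, and 6.4.1.2 gives a dating rule for ASTRO failure.

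Section 7.3.1.2 bases the efficacy verdict on a one-sided 95% Wilson lower limit L. Its inputs are "p: the observed proportion of patients experiencing bDFS" and "n: the total number of patients". Efficacy is declared if the study's "result verifies that L is not below 92" per cent. Section 7.3.1.1 uses the matching upper limit U for grade 3-5 toxicity, and safety is declared if the study's "result verifies that U is not above 10" per cent. Section 7.3 describes the safety objective as "gastrointestinal and genitourinary toxicity observed during an initial 24 month follow up".

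Section 7.3.2.3 begins "Survival analyses will be performed for the following quantities" and lists disease-free, disease-specific and overall survival. Neither bDFS nor toxicity is on that list. The plan's one remark on missing data (7.3.2.1) concerns GEE models for secondary endpoints. Section 7.2 plans 200 eligible patients and makes no allowance for loss. Section 8.1.1 allows removal for withdrawal, serious illness, protocol violation or investigator discretion, among other reasons.

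**The concern.** A man who withdraws, dies without PSA failure, is removed, or misses the 24-month PSA has been followed for part of the window only. A crude proportion cannot represent that, and the plan does not say how he enters p or n. The efficacy margin is narrow, so the unstated choice can move the primary verdict, and it could be made after the data are seen.

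Taken literally, the two formulas also push in opposite directions. A man not observed to be free of failure is not an efficacy success, which is conservative. Toxicity after he is lost is never seen although he remains in n, which favours a safe verdict.

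**Working it through.** **Inputs.** n = 200 (7.2.3). Z = 1.645 and the 92% and 10% lines (7.3.1). True bDFS of 97% or 96% (7.2.2), tested "with 80% power at the 1-sided 5% significance level". Assumed, because the documents give no figure: a fraction q of men is lost, with loss times uniform over 24 months and exponential failure times.

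**Cut-offs.** L or U = [(2np + Z²) ∓ Z√(Z² + 4np(1−p))] / [2(n + Z²)].
- 191/200: (384.706 − 10.018)/405.412 = 92.4%, pass.
- 190/200: (382.706 − 10.495)/405.412 = 91.8%, fail.
- 13/200 toxicities: (28.706 + 11.785)/405.412 = 9.99%, safe.
- 14/200 toxicities: (30.706 + 12.176)/405.412 = 10.58%, not safe.

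**The plan's power.** The exact probability P(X ≥ 191) is 91.9% at 97% and 71.9% at 96%; at 92% it is 3.7%. Section 7.2.2 states 99% and 78%, which this rule does not reproduce. The same sentence also gives 80%. That is a separate matter, and the loss calculations below start from 91.9%.

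**Efficacy with loss.**
- Lost men not successes: success probability = 0.97(1−q). At q = 2% this is 0.9506, or 200 × 0.0494 = 9.9 expected non-successes. At q = 5% it is 0.9215, or 15.7 expected, against 9 tolerated.
- Lost men successes: observed failure probability ≈ (1−S)(1−q/2). At 97% and q = 5% this is 0.0293. At 92% and q = 10% it is 0.0761.
- Lost men excluded: the number excluded is binomial (probability 0.0492 at q = 5%), the cut-off is recomputed at 200 minus that number, and the success probability is 1 − 0.0293/0.9508 = 0.9692.
- Kaplan-Meier with a Wilson limit on the effective n: 20,000 simulated trials.

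| Handling | Pass at 97%: no loss | 2% lost | 5% lost | Pass at 92%: no loss | 10% lost |
|---|---|---|---|---|---|
| Not successes | 91.9% | 47.0% | 4.4% | 3.7% | ~0 |
| Successes | 91.9% | 92.3% | 92.9% | 3.7% | 5.6% |
| Excluded | 91.9% | 92.3% | 90.5% | 3.7% | 2.8% |
| Kaplan-Meier | ~92% | ~93% | ~93% | ~4% | ~4% |

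Simulating the second row gave about 3.9% and 5.9% at a true 92%, in place of the calculated 3.7% and 5.6%. The drift is the same.

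**One data set.** Take 6 failures (0, 1, 1, 2, 2 at months 3, 6, 12, 18, 24) and 4 men lost, one before each of the last four visits. If the lost men are not successes, the result is 190/200, L = 91.8%, fail. Kaplan-Meier gives S = (198/199)(196/197)(193/195)(190/192) = 96.96%. The effective n is S(1−S)/(Greenwood variance) = 197.1, so L = 94.2%, pass. With 20 lost, L = 93.8%, pass.

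**Safety at a true 10%.** Let k men be lost, with a fraction h of their events before loss. Then P(safe) = P(Bin(200−k, 0.10) + Bin(k, 0.10h) ≤ 13).
- k = 0: 5.7%.
- k = 10: 7.0% at h = ½; 8.7% at h = 0.
- k = 20: 8.7% at h = ½; 12.9% at h = 0.

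The h = 0 figures are upper bounds.

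**The case against.** The strongest reply is that 7.3.1 does not say what happens to a lost man, so the steep fall in power comes from one reading only. That is right. A reader might infer that each lost man must be scored as a failure or a success. The documents do not force this: the denominator is not stated to be 200, 7.2.3 speaks of eligible patients, and 7.4 divides by participants evaluated. Exclusion is a third reading. Under it, 59 men would have to be dropped to turn 6 failures into a fail. If exactly 10 men are dropped, the cut-off is 181/190 and power at 97% is 93.8%.

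A reader might also infer that both primary endpoints are time-to-event measures, or that every man lost counts as free of toxicity. Neither is supported. Only bDFS is defined as a time; toxicity is a rate within a window. Section 6.1.4 schedules toxicity checks from one week after treatment onward, and an event seen before loss is counted. Some 8.1.1 removals, such as biochemical progression or grade 4 GI/GU toxicity, are themselves endpoint events.

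Partial mitigation exists. Disease-free survival, which includes PSA failure, already gets Kaplan-Meier curves with two years as an example time. Follow-up of at least five years may also supply a later PSA for a missed visit. But neither of these enters the efficacy rule, and no handling rule is given for it.

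**Conclusion.** The point stands as a should-fix. The efficacy statistic does not match its own definition, and the plan leaves open a choice that moves the pass probability at 97% between 4–5% and about 93% at 5% loss. That spread shows what the missing rule could do. It is not the expected effect, since it arises only if lost men are not successes; the other readings move power by a point or two.

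For safety the bias is one-sided while lost men stay in n, but it is modest: 5.7% to about 7–9% for 10–20 lost if half their events precede loss, and at most 8.7–12.9%. If men are excluded instead, the direction can reverse: 13/200 is safe, while 13/199 gives U = 10.04% and is not.

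It would be too much to say that a few men always decide the result. That holds close to the cut-offs, or when lost men are scored adversely. All loss figures are assumptions.

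**What to change.** In 7.3.1.2, define p as the Kaplan-Meier estimate of bDFS at 24 months, censoring men without failure at their last PSA. Compute L by the existing Wilson formula with n replaced by the Greenwood effective n. With no loss the effective n equals n, so the present rule is recovered. Keep the 92% line.

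In 7.3.1.1, define p as the 24-month cumulative incidence of first grade 3-5 GI/GU toxicity, with death as a competing event and the same effective-n Wilson limit. Keep the 10% line. A log-log limit would not be neutral: at 13/200 with no loss it gives 10.06% and would lower the allowed count from 13 to 12.

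Add a sensitivity analysis that counts lost men as failures for efficacy and as toxic for safety. Both main estimates assume that censoring is unrelated to outcome, which is doubtful for some 8.1.1 removals.

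The cost is SAP wording and a software estimate in place of a closed formula. The PSA and toxicity visits in 6.1.4 already supply the data. Kaplan-Meier is already in the plan; cumulative incidence would be new to it, though routine. The fix does not remove closeness at the line: 9 failures with 20 lost gives L = 91.8%, and 13 toxicities with one man lost gives U = 10.02% (events and losses assumed spread over the visits).

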### 7.3.2 SECONDARY ENDPOINTS

#### 7.3.2.1 MEASUREMENTS OF RATE OF LOCAL FAILURE

AND RATE OF DISTANT FAILURE: The PSA levels are used to quantify the rate of local and distant failures repeatedly during the post treatment period. The GEE (Generalized Estimating Equation) method will be used to

provide valid inferences. This method was originated to make inference about average behaviour, where the dependent variable depends not only on the “explanatory” variable (time measured in months) but also on the correlation of a patient’s repeated measurements. The GEE approach fits the model to the observed data as closely as possible, weighting each patient’s “cluster” of measurements over time inversely to its variance-covariance matrix. With this method, no imputations are required and all data recorded is used in the analysis. Other important features of GEE are that no distributional assumptions for the dependent variable are required to use the method and in most cases valid inferences are provided even when the correlation structure is miss-specified. For each PSA level, we will use GEE to fit a model to patients’ longitudinal course of repeated values.

7.3.2.2 **QUALITY OF LIFE ASSESSMENTS:** The FACT-G scores, AUA score, EPIC-26 scores are used to quantify quality of life (QOL) at baseline and repeatedly during the post treatment period. Similarly to measurements of local and distant failure rate, we will still use the GEE method to provide valid inferences. For each score, we will use GEE to fit a model to patients’ longitudinal course of repeated values. We hypothesize that immediately following treatment, the GU & GI subsections of the EPIC-26 and the AUA will demonstrate a worsening of GU and GI function, but this will return to normal with time. We further hypothesize that the sexual function subset of the EPIC-26 will show gradual worsening function relative to baseline over the five-year follow-up period. These QOL outcomes will be compared to those reported in other prospective studies using the same instruments, including RTOG 0232 and 0415.

7.3.2.3 **SURVIVAL ANALYSIS:** Survival analyses will be performed for the following quantities:

- Rate of disease-free survival;
- Rate of disease-specific survival;
- Overall survival for death from any cause;

Periodically over the extended follow-up period, Kaplan-Meier “survival” curves will be calculated (examples: at 6 months, yearly, 2 years, at end of patient follow-up). From the Kaplan-Meier curve, descriptive statistics will be calculated including estimates of survival rates and mean and quartile survival times.

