6.4.1.1 Phoenix definition: failure occurs when the PSA is  $\geq 2$  ng/ml more than the lowest PSA measurement before the current one, with no backdating. Administration of salvage therapy (hormones, surgery, etc...) will be considered failure.

6.4.1.2 Strict ASTRO Consensus Definition (ACD): failure is defined as three consecutive rises in post-treatment PSA, measured at the specified follow-up intervals. If three consecutive PSA rises occur during the first 2 years after treatment, followed by a non-hormonal induced PSA decline, this will not be considered a failure. Administration of salvage therapy (hormones, surgery, etc...) will be considered failure. Failure date is the midpoint between the dates of the last non-rising PSA and the first PSA rise.

6.4.2 CRITERIA FOR **LOCAL FAILURE** (Secondary Objective): clinical evidence of local progression or recurrence. Clinical

failure includes a palpable abnormality that has increased in size, failure of regression of a palpable abnormality by 2 years after treatment, or redevelopment of a prostate abnormality after complete response. Patients with a prostate abnormality compatible with local recurrence, or a PSA failure shall undergo a prostate biopsy. Histologic criteria for local failure is a positive prostate biopsy more than 2 years after treatment. Patients with a normal exam and no evidence of PSA failure shall be considered controlled locally. Patients with clinical failure and no biopsy are

considered local failures. If a patient is locally controlled at the time of orchiectomy or androgen ablation, he is censored and considered “not evaluable” for further local control.

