##### 6.4.3.1 **DISTANT FAILURE** (includes regional failure)

documented if clinical, bone scan, CT or other imaging study shows metastatic disease. Biochemical failure with a negative prostate biopsy shall be considered distant only failure. Biopsy of metastatic site required if radiographic or clinical findings are equivocal. Type of metastatic failure (distant and/or regional) shall be recorded if known.

Prostate biopsy recommended at this time.

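### Section 7.3.2.1 analyses local and distant failure only through a GEE on PSA level, which yields neither 2-year proportion and cannot separate the two sites

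*Combined protocol and SAP*

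**What the plan says.** The Protocol Summary and section 7.3 define the two endpoints as the "proportion of patients with local disease progression at 2 years" and the "proportion of patients with metastatic disease at 2 years".

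Section 6.4.2 bases local failure on palpable or other clinical findings and on biopsy. It adds three rules:
- "Patients with a normal exam and no evidence of PSA failure shall be considered controlled locally".
- "Histologic criteria for local failure is a positive prostate biopsy more than 2 years after treatment".
- "If a patient is locally controlled at the time of orchiectomy or androgen ablation, he is censored", and is then not evaluable for further local control.

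Section 6.4.3.1 documents distant failure by clinical or imaging evidence of metastatic disease, and adds: "Biochemical failure with a negative prostate biopsy shall be considered distant only failure".

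Section 7.3.2.1 covers both endpoints with one method. It states: "The PSA levels are used to quantify the rate of local and distant failures repeatedly during the post treatment period". It describes GEE as a method for average behaviour, names time in months as the explanatory variable, and says that all recorded data are used. It ends: "For each PSA level, we will use GEE to fit a model to" each patient's repeated values.

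The Wilson intervals in 7.3.1 are applied to the two primary endpoints. The Kaplan-Meier analyses in 7.3.2.3 list disease-free, disease-specific and overall survival only.

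**The concern.** The endpoints are event proportions by site, but the planned model describes a mean biomarker level. Nothing in 7.3.2.1 turns a fitted PSA curve into a count of men with local progression or with metastases, and one PSA series gives one fit for both. Followed as written, the plan would report a PSA trend where two named secondary endpoints belong. The actual counting method would then be settled after the data are seen.

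Two related gaps add to this. First, 7.3.2.1 does not carry over the censoring rule of 6.4.2, which applies to local control only. PSA values recorded after salvage hormones could enter the model and make failed men look controlled. Second, the histologic criterion in 6.4.2 does not fit a reading at 2 years, so some men may have no defined local status.

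**Working it through.** The plan states no expected rate, power or sample size for local or distant failure, so there is no figure to reproduce. The check has three parts.

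**1. What each section supplies**

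| Needed for a 2-year site-specific proportion | In 6.4.2 / 6.4.3.1 | In 7.3.2.1 |
|---|---|---|
| Yes/no failure status | Yes | No; PSA values |
| Separation of local from distant | Yes, by examination, biopsy and imaging | No; one PSA series |
| 2-year time point | In the endpoint definition (7.3) | No; time in months only |
| Censoring at orchiectomy or androgen ablation (local only) | Yes (6.4.2) | Not mentioned |

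**2. Can mean PSA identify even the PSA-failure proportion?**

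From the protocol: n = 200 (7.2.3); PSA at 3, 6, 12, 18 and 24 months (6.1.4); the Phoenix rule, a PSA at least 2 ng/ml above the lowest earlier value (6.4.1.1). The PSA values are assumed. Men without failure have 2.0, 1.2, 0.8, 0.6 and 0.5 ng/ml.

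- Scenario A: 4 men have +5 at 18 months and +10 at 24 months. Each reaches 0.6 + 5 = 5.6 at 18 months, which is 4.8 above the earlier low of 0.8, so all fail: 4/200 = 2%.
- Scenario B: 16 men have +1.25 and +2.5. Each reaches 0.5 + 2.5 = 3.0 at 24 months, which is 2.2 above 0.8, so all fail: 16/200 = 8%.

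Total excess PSA:
- at 18 months, 4 × 5 = 16 × 1.25 = 20, or 20/200 = 0.10 on the mean;
- at 24 months, 4 × 10 = 16 × 2.5 = 40, or 40/200 = 0.20 on the mean.

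Visit means are therefore 2.0, 1.2, 0.8, 0.7 and 0.7 in both scenarios.

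With complete visits and linear time, the coefficients follow from these means. Mean time is 12.6 months and mean PSA is 1.08. The sum of cross-products is −15.84 and the sum of squares of time is 295.2.
- Slope = −15.84 / 295.2 = −0.05366 per month.
- Intercept = 1.08 + 0.05366 × 12.6 = 1.7561.

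Fitted GEEs gave these values in both scenarios, under independence and exchangeable working correlation. With time as a category, the coefficients are 2.0, −0.8, −1.2, −1.3 and −1.3 in both. Only the robust standard errors differ (slope: 0.0047 in A, 0.0023 in B). They are smaller where there are more failures and do not estimate a proportion. Relabelling the failing men as local or distant leaves the data, and so the whole fit, unchanged.

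A second set of assumed values (visit means 2.00, 1.20, 0.80, 0.75, 0.80) behaved the same way: 0, 10 or 20 PSA failures in 200 all gave intercept 1.7259 and slope −0.0489.

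**3. Status of a man with an early positive biopsy**

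Section 6.1.5 has a biopsy done at biochemical failure. Take a man with PSA failure, a normal examination and a positive biopsy at 18 months:
- He does not meet the histologic criterion for local failure, because the biopsy is not more than 2 years after treatment.
- He has no clinical local failure.
- He does not meet the stated condition for local control, because PSA has failed.
- He is not classed as distant-only, because that requires a negative biopsy.

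No sentence gives him a local status at 2 years. Men with clinical failure are still counted.

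**What a direct count would give**

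Two-sided 95% Wilson limits, z = 1.96: [2np + z² ± z√(z² + 4np(1−p))] / [2(n + z²)], for assumed counts in 200 evaluable men:

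| Failures | Proportion | 95% interval |
|---|---|---|
| 0 | 0% | 0.0–1.9% |
| 2 | 1% | 0.3–3.6% |
| 6 | 3% | 1.4–6.4% |
| 10 | 5% | 2.7–9.0% |

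**The case against.** **The endpoint definition is already an estimator.** Section 7.3 calls each rate a proportion of patients at 2 years, and nothing says that the GEE replaces that count. A GEE on a binary failure indicator could also estimate a proportion, so this may be loose drafting. It may be, but 7.3.2.1 presents PSA as the measure of both rates and models repeated values, and 7.3.2.2 applies the same approach to quality-of-life scores. The binary reading is not in the text, and no interval method is given for either proportion.

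**The status gap is overstated.** The local-control sentence in 6.4.2 is a sufficient condition only, so a man with PSA failure could be read as not yet a local failure. A bone scan at biochemical failure (6.1.6) can settle his distant status. The logical point is fair. Still, that reading has to be supplied by the analyst, because no passage assigns his local status.

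**The illustration is constructed.** The PSA values were chosen to force equal means, and they vary PSA failure rather than site-specific failure. This stands as a limit: the example shows that the mean model cannot identify the proportion, not how large an error this trial would see.

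**The hormone effect may be small.** Section 6.4.1 counts salvage therapy as failure, though for bDFS and not for the GEE. Disease progression is also a removal criterion (8.1.1) and may end data collection. The size cannot be judged from the documents.

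**These are secondary endpoints** with no hypothesis or decision rule. That bears on priority, not on whether the method fits.

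**Conclusion.** The concern holds. The only stated analysis of local and distant failure estimates mean PSA over time. It gives neither 2-year proportion and cannot tell the sites apart. This follows from the structure of the model and does not depend on the assumed PSA values; those only show that 2% and 8% PSA failure can produce the same coefficients. The early-biopsy gap is a separate definitional point, and the number of men affected is unknown. The primary safety and bDFS rules in 7.3.1 and the sample size are unaffected. The plan should be changed, because two named secondary endpoints otherwise have no valid planned analysis.

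**What to change.** Amend 7.3.2.1 as follows:

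1. Analyse failure status as defined in 6.4.2 and 6.4.3.1, separately for local and distant failure. Report each 2-year proportion with a two-sided 95% Wilson interval. The Wilson form is already in 7.3.1, where it is one-sided with z = 1.645; the two-sided version uses z = 1.96.
2. Where follow-up is incomplete, use cumulative incidence from first treatment with death as a competing event. Death may matter little by 2 years, given the 10-year life-expectancy criterion.
3. Apply the 6.4.2 censoring rule to local control and report how many men it removes, since this censoring may be informative.
4. Reconcile the histologic timing in 6.4.2 with the 2-year reading and with biopsy at biochemical failure in 6.1.5, so that every man has a status.
5. Keep the PSA GEE as a separate descriptive analysis of PSA before salvage therapy, noting that stopping at salvage selects men on their PSA course.
6. Report later estimates only as follow-up allows, since visits after year 2 are optional (section 6.0, note b).

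The cost is some SAP wording and modest analysis work. Examination, PSA, biopsy at failure and imaging when indicated are already planned, so no patients or visits are added. One condition applies: the team should confirm that removal for disease progression under 8.1.1 does not stop collection of failure status up to 2 years.
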